Doses will be escalated in the standard 3 + 3 fashion, starting with 5 x 10^9 colony forming units (CFU) to a maximum dose level of 1 x 10^{10} CFU. Dose cohorts of 3 subjects each will be treated. In the absence of dose-limiting toxicity (DLT) as defined in Section 6.1 Dose Limiting Toxicity assessed during the first treatment cycle, the dose will be escalated to the next dose level for the next 3 subjects. If DLT is seen in 1 of 3 subjects, another 3 subjects will be treated at that same dose. If DLT is seen in 2 of 6 subjects, then that dose level will be considered maximum tolerated dose (MTD) and the previous dose level will be selected as the recommended Phase 2 dose (RP2D). The RP2D will be selected based on an observed DLT rate of < 33%.

Treatment cycles can be repeated at the RP2D (or less) for an individual subject until a discontinuation criterion is met. Discontinuation criteria include documented disease progression, intolerable side effects not resolved with dose reduction or change in premedications or the subject completes 1 cycle of treatment post observation of complete response (CR) per RECIST 1.1 and immune-related RECIST criteria (irCR).

Sponsor:	Name of Finished Product:	Type of Treatment:
Advaxis, Inc.	ADXS11-001	Lm-LLO Immunotherapy

Further assessment of the RP2D level may be explored in an expansion cohort in subjects with persistent, metastatic, or recurrent carcinoma of the cervix who have failed conventional therapy to evaluate the safety and clinical activity of ADXS11-001. Treatment will continue for each subject until a discontinuation criterion is met. The end of treatment will be defined as 1 year after the last subject's first treatment or until that subject has met a discontinuation criterion. All subjects will be followed for adverse events (AEs) and serious adverse events (SAEs) from the time written informed consent is signed through the completion of the *Lm* surveillance period.

Safety will be assessed by comparing treatment-related AEs, changes in physical examinations, vital sign measurements, laboratory abnormalities and *Lm* surveillance monitoring.

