DLTs will only be assessed during the first 28 days in cycle 1 (See Section 6.1, Dose Limiting Toxicity Criteria, for DLT definition). Transient hypotension which may require IV fluids for management is an expected event that subjects may experience with ADXS11-001 infusions. Subjects with signs of cytokine release symptoms ≥Grade 3 (per CTCAE v 4.03) that persist for more than 24 hours despite symptomatic treatment, will be judged to have a DLT. Blood cultures will not be obtained on a routine basis but will be collected in subjects who have persistent fever 24 hours after the end of ADXS11-001 infusion. Subjects will receive a 7-day course of either oral 80 mg trimethoprim / 400 mg sulfamethoxazole once daily or 160 mg trimethoprim / 800 mg sulfamethoxazole (DS) 3 times over the course of the 7 days. Subjects with known allergy to sulfa drugs may receive ampicillin 500 mg 4 times daily for 7 days beginning on Day 4 (approximately 72) hours) after each study treatment infusion. A subject who experiences a fever (CTCAE Grade 1 or greater) 24 hours following the completion of ADXS11-001 infusion should be started on NSAIDS, hydration and other appropriate measures to treat the fever. In the event that the fever persists or worsens 48 hours following the completion of ADXS11-001 infusion then oral or broad spectrum IV antibiotics should be considered based on the subject's medical condition. If the fever remains unresponsive to oral/IV antibiotics 72 hours following the completion of the infusion then a blood culture should be obtained to evaluate for listeremia and determine the appropriate treatment course for the subject. Study cycles can be repeated at the RP2D (or less) for each subject until a discontinuation criterion is met. Criteria include documented disease progression, intolerable side effects not resolved with dose reduction or change in pre-medications, or the completion of 1 cycle of treatment post observation of complete response per RECIST 1.1 and immunerelated RECIST criteria (irCR).

Safety will be assessed by comparing treatment-related AEs, changes in physical examinations, vital sign measurements, and laboratory abnormalities.

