Immunologic effects will be measured and evaluated by collection of peripheral blood for preparation of peripheral blood mononuclear cells (PBMCs) and serum immediately prior to each ADXS11-001 infusion and 2 weeks after every ADXS11-001 infusion in Cycle 1 only (Day 1 of Weeks 3, 6, 9, and 12). PBMCs will be analyzed for the presence and quantitation of HPV-E7 and HPV-E6 specific CD8+ T-cells through ELISpot and other assays as well as Treg cells and MDSCs. PBMC immunologic gene expression analysis may also be conducted. Serum will be evaluated for serum cytokines, chemokines, and other potential markers. Blood will be collected in Cycle 1 only at 3 time points immediately prior to each ADXS11-001 infusion and 2 hours and 4 hours post infusion (±15 minutes- Day 1 of Weeks 1, 4, 7, and 10).

Subjects should arrive at the study center on the days of their scheduled ADXS11-001 administration in order to be evaluated, have laboratory specimens collected before treatment commences, and complete the study prophylactic regimen at least pre-infusion before receiving the ADXS11-001 infusion.

Subjects will remain at the study site for a minimum of 4 hours after the infusion for safety observations, and if necessary treatment of side effects resulting from the study treatment administration. Treatment and observation of side effects may take up to an additional 4 hours, so subject arrival at the study center should be early enough to accommodate a possible 9-hour visit day. Vital signs will be taken pre-dose then every after the infusion as a safety measure.

After the initial study cycle, subjects who respond or have immune-related SD at or after tumor assessments may receive additional treatment at the same dose and schedule, until either evidence of disease progression, intolerable side effects not resolved with dose reduction or change in premedications, or for 1 completed study cycle post achievement of CR per RECIST 1.1 and immune-related RECIST criteria (irCR). These subjects may continue to be evaluated for response every 12 weeks.

Study treatment will be modified as per Table 11 in Section 11.6.1 Treatment Modification Guidelines.

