9.1.10 Best Overall Response (RECIST 1.1)

The best overall response is the best response recorded from the start of the study treatment until the end of treatment taking into account any requirement for confirmation. The subject's best overall response assignment will depend on the findings of both target and non-target disease and will also take into consideration the appearance of new lesions (Table 7).

Table 7 Best Overall Response (RECIST 1.1)

Target Lesions	Target Lesions Non-Target Lesions		
Baseline (Index) and New Measurable Lesions	Baseline Lesions	Baseline Lesions Unequivocal New Lesions	
CR	CR	No	CR
CR	Non-CR/Non-PD	No	PR
CR	NE	No	PR
PR	Non-PD or NE	No	PR
SD	Non-PD or NE	No	SD
Not all evaluated	Non-PD	No	NE
PD	Any	Yes or No	PD
Any	PD	Yes or No	PD

a Subjects with an initial finding of progressive disease (irPD) before or at the 12-week imaging assessment, but without rapid clinical deterioration, require confirmation of irPD with a second, consecutive scan obtained ≥ 4 weeks from the initiation documentation. Subjects will continue to receive study treatment until irPD is confirmed at this later time point. Best overall response (BOR) will therefore include responses occurring at any time before disease progression and after early progression (i.e., within the first 12 weeks of the study).

Target Lesions	Non-Target Lesions		
Baseline (Index) and New Measurable Lesions Baseline Lesions		Unequivocal New Lesions	Overall Response
Any	Any	Yes	PD

CR = complete response; NE = not evaluable at a particular time point; PR = partial response; SD = stable disease; PD = progressive disease

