9.1.12 Treatment after Initial Evidence of Radiologic Disease Progression

Immunotherapy may produce antitumor effects by potentiating endogenous cancerspecific immune response. The response patterns seen with such an approach may extend beyond the typical time course of responses seen with cytotoxic agents and can manifest as a clinical response after an initial increase on tumor burden or even the appearance of new lesions. If radiological imaging shows PD, subjects may continue on study with the option of continuing treatment, provided there is:

- No deterioration in ECOG performance status
- Absence of signs and symptoms (including worsening of laboratory values) indicating disease progression
- Absence of rapid progression of disease
- Absence of progressive tumor at critical anatomical sites (e.g., cord compression) requiring urgent alternative medical intervention

Tumor assessment should be repeated ≥4 weeks later to confirm PD. If repeat imaging shows a reduction of in the tumor burden demonstrating CR, PR or SD compared to the initial scan, treatments may be continued or resumed. If repeat imaging shows continued progression of disease, subjects will be discontinued from study therapy, unless the basis for the PD assessment is enlarged tumor-draining lymph nodes in the presence of a target tumor reduction. In determining whether or not tumor burden has increased or decreased, investigators should consider all target lesions as well as non-target lesions. If the repeat imaging confirms initially documented PD but shows no evidence of further tumor progression, subjects should be discontinued from the study treatment.

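### For a first, unconfirmed irPD at the Week 12 scan, three parts of the protocol conflict on whether infusions continue

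*Combined protocol and SAP*

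**What the plan says.** Three texts in the combined protocol and SAP deal with treatment once a scan shows progression.

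- **Section 6** (treatment after the initial cycle): "After the initial study cycle, subjects who respond or have immune-related SD at or after tumor assessments may receive additional treatment". The sentence then sets the end point: subjects "may receive additional treatment at the same dose and schedule, until either evidence of disease progression", or until one of two other end points, intolerable toxicity or one further cycle after complete response.
- **Table 6, footnote a**: "Subjects with an initial finding of progressive disease (irPD) before or at the 12-week imaging assessment, but without rapid clinical deterioration, require confirmation" by a second scan at least 4 weeks later. On treatment in the meantime it says: "Subjects will continue to receive study treatment until irPD is confirmed at this later time point".
- **Section 9.1.12**: "If radiological imaging shows PD, subjects may continue on study with the option of continuing treatment, provided there is" a stable performance status, no clinical or laboratory signs of progression, no rapid progression, and no growth at a critical site. It sets no Week 12 limit, and it allows treatment to be held and then resumed after the repeat scan.

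A fourth wording appears twice. The Synopsis says "Discontinuation criteria include documented disease progression, intolerable side effects not resolved with dose reduction", and Section 6 repeats it: "Criteria include documented disease progression, intolerable side effects not resolved with dose reduction or change in pre-medications". Neither says whether progression counts as documented at the first scan or only once confirmed.

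Section 9.1.6 defines irPD as growth in total measurable tumor burden of at least 20% over nadir, and irSD as a state without irPD. Confirmation is not part of either definition.

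**The concern.** Week 12 is the first scheduled scan after baseline, so it is where entry to cycle 2 is decided. A subject with irPD on that scan who is clinically stable is an ordinary case. Section 6 does not include this subject among those who may go on, footnote a says treatment will go on, and Section 9.1.12 leaves it to choice under four conditions. No text says which prevails, and the Section 6 wording cites neither of the other two. In a multi-center trial, sites can reasonably act differently on the same scan.

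At stake is how much of a live attenuated Listeria product a subject receives after first progression, and every quantity tied to the last dose: the window for summarizing adverse events (Section 14.5.4), the 6-month antibiotic course (Section 8.1, item 16) and the Lm surveillance schedule (Table 5, footnote 19).

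**Working it through.** The plan gives no figure to reproduce. The check applies each text to one case and then counts infusions on the calendar.

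**Case:** first irPD at the Week 12 assessment, unconfirmed, no rapid clinical deterioration.

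| Text | Further infusions? | Conditions | Time limit |
|---|---|---|---|
| Section 6, after cycle 1 | Not offered: the subject is neither a responder nor irSD | none | none |
| Table 6, footnote a | Yes, until irPD is confirmed | no rapid clinical deterioration | irPD up to and including Week 12 |
| Section 9.1.12 | Optional | four | none |
| Synopsis and Section 6, documented progression | Undetermined | none | none |

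The second and third rows also conflict with each other. A subject whose performance status has declined, but without rapid deterioration, is kept on treatment by the footnote and fails the first condition of Section 9.1.12. For irPD first seen after Week 12 the footnote no longer applies, and the conflict is between Section 6 and Section 9.1.12.

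**Inputs for the count**
- Infusions: Day 1 of Weeks 1, 4, 7 and 10 of each 12-week cycle (Section 6). Study week = 12 × (cycle − 1) + week in cycle, so cycle 2 falls at Weeks 13, 16, 19 and 22.
- Scan: Week 12 ± 1 (Table 5, footnote 20), so week s = 11, 12 or 13.
- Confirmation: L weeks later. L is at least 4 in Table 5 footnote 20, Section 8.1 item 17, Table 6 footnote a and Section 9.1.12, but 3 to 4 in Section 8.3.

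**Infusions between scan and confirmation under footnote a.** The first number counts infusion weeks from s up to but not including s + L. The second also counts week s + L.

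| Scan week | L = 3 | L = 4 | L = 5 |
|---|---|---|---|
| 11 | 1 / 1 | 1 / 1 | 1 / 2 |
| 12 | 1 / 1 | 1 / 2 | 2 / 2 |
| 13 | 1 / 2 | 2 / 2 | 2 / 2 |

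For a Week 12 scan and L = 4, confirmation falls in Week 16: the Week 13 infusion is given, and the Week 16 infusion depends on whether it precedes the scan result. Two is not a ceiling, because at least 4 weeks has no upper limit: a Week 13 scan confirmed 6 weeks later, in Week 19, gives 2 / 3. The count assumes the scan precedes any infusion in its own week and ignores the ±7-day infusion window.

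**Effect on last dose.** Day 1 of Week w is study day 7(w − 1) + 1.

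| Last infusion | Study day | Day + 30 |
|---|---|---|
| Week 10 | 64 | 94 |
| Week 13 | 85 | 115 |
| Week 16 | 106 | 136 |

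One or two extra infusions move the end of the adverse event summary window by 85 − 64 = 21 or 106 − 64 = 42 days. The first surveillance assessment, set 3 months after the last dose, moves by the same amount. Against four cycle 1 infusions, exposure rises by 1/4 = 25% or 2/4 = 50% for that subject.

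**The case against.** The strongest reply is that Section 9.1.12 is the dedicated rule, with conditions, a repeat scan and an outcome for each result, and that Section 8.1 item 17 points to it straight after the sentence on confirming apparent progression. On this view Section 6 is the general description and footnote a merely annotates a response table. Section 11.8.1 also lists disease progression as a reason for which a subject may, not must, be discontinued.

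Part of this stands. Section 6 excludes the subject through its description of who may continue and when that ends. A reader might infer an order to discontinue, but the text contains none. A reader might also infer that the Synopsis stops treatment at the first scan, giving 0 infusions there too. The documents do not support that as a finding: the term is undefined and could mean confirmed progression. Section 9.1.12 does describe progression on the first scan as already documented, but one usage does not settle the Synopsis.

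The reply does not remove the conflict. Giving Section 9.1.12 precedence still leaves the footnote's mandatory wording and single condition against an option with four conditions, and nothing in the protocol grants that precedence.

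A further fair limit is that the contrast with Section 6 turns on irPD. A subject with RECIST 1.1 progression from a new lesion but less than 20% growth in total burden could be irSD under Section 9.1.6 and so remain eligible, although Table 8 rates any unequivocal new lesion as irPD.

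**Conclusion.** The contradiction is real and is an error in the text as written, not a missing detail. For a clinically stable subject with a first irPD at Week 12, the Section 6 wording gives 0 further infusions. Footnote a gives 1 or 2 if confirmation comes about 4 weeks later, and more if it comes later still. Section 9.1.12 allows either course. The count rests on the nominal infusion calendar and the assumptions stated with it.

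Three larger readings are not supported:
- **A share of subjects affected.** The documents give no progression rate at Week 12, and subjects with rapid clinical deterioration would have to be removed from any such rate. The size can be stated only per subject.
- **A threat to the dose decision or the analysis sets.** DLTs are assessed only in the first 28 days (Section 6.1), so DLT assessment and RP2D selection are unaffected. The efficacy population requires one completed cycle (Section 14.5), which does not depend on cycle 2 treatment.
- **Loss of later immune-related responses from irBOR.** Section 9.1.11 already bars a later irCR, irPR or irSD as irBOR after irPD at Week 12, whichever treatment rule applies; later activity is exploratory.

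Adverse events are collected through the 3-year surveillance period in any case, so it is the summary window that moves, not collection. The analysis is descriptive, and no test is affected.

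**What to change.** Reconcile the Synopsis, both statements in Section 6, Table 6 footnote a and Section 9.1.12 into one rule for treatment after first progression. It should state:

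- whether continuation is required or optional, and under which conditions;
- whether it is limited to progression found up to Week 12;
- whether documented progression means the first or the confirmed finding.

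Section 6 and the Synopsis should cite that rule and not restate it. Two neighboring texts should be aligned at the same time. Section 9.1.11 treats irPD at Week 12 as final for irBOR, while footnote a requires it to be confirmed. Section 8.3 gives a confirmation interval of 3 to 4 weeks, against at least 4 weeks elsewhere.

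Which clinical rule should apply is for the sponsor and investigators; this point takes no position. The cost is amended wording only, with no added visits, scans or samples.

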11.6.1 Treatment Modification Guidelines

The dose of ADXS11-001 will not be modified (e.g., reduced or increased). However, treatment may be delayed or discontinued for drug related severe and life-threating toxicities, as shown below in Table 11.

Table 11 Treatment Delay/Discontinuation Guidelines for Drug-Related Adverse Events

Toxicity	Grade	Hold treatment	Timing for restarting treatment	Discontinue Treatment
	1,2,3	No	N/A	N/A
Hematologic	4	Yes	Toxicity resolves to ≤Grade 1 or baseline	Toxicity does not resolve to ≤Grade 1 or baseline within 12 weeks
	1	No	N/A	N/A
Non- hematologic, excluding cytokine release symptoms and DLTs	2-3	Yes	Toxicity resolves to ≤Grade 1	Toxicity not resolved to ≤Grade 1 within 12 weeks of last infusion ^a
	4	N/A	Permanent treatment discontinuation	Permanent Discontinuation from Treatment

^a With investigator and sponsor agreement, subjects with a non-hematologic AE (e.g. alopecia, neuropathy) still at grade 2 after 12 weeks, may continue treatment if only asymptomatic and controlled.

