11.6.2 ADXS11-001 Treatment Alterations

Subjects who experience a DLT during the dose escalation portion of the study or experience events described as a DLT in any subsequent treatment cycle will be discontinued from study treatment. However, if the subject who experienced a DLT shows significant response to ADXS11-001, they may be eligible to receive ADXS11-001 at a lower dose level for subsequent doses and cycles following discussion and agreement between the Investigator and Sponsor. See Section 6.1 Dose Limiting Toxicity Criteria for definition of DLT.

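### Repeat cycles are capped at the RP2D in two places but allowed at an unchanged dose in a third, so a DLT-free subject on a rejected dose level could be re-dosed above the RP2D

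*Combined protocol and SAP*

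**What the plan says.** Four statements govern the dose after cycle 1.

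- **Synopsis, Methodology:** "Treatment cycles can be repeated at the RP2D (or less) for an individual subject until a discontinuation criterion is met". When 2 of 6 subjects have a DLT, "the previous dose level will be selected as the recommended Phase 2 dose (RP2D".
- **Section 6, paragraph on DLT assessment:** "Study cycles can be repeated at the RP2D (or less) for each subject until a discontinuation criterion is met".
- **Section 6, paragraph on treatment after the initial cycle:** subjects who respond or have immune-related stable disease "may receive additional treatment at the same dose and schedule". The section then closes with "Study treatment will be modified as per Table 11 in Section 11.6.1 Treatment Modification Guidelines".
- **Section 11.6.1, introducing Table 11:** "The dose of ADXS11-001 will not be modified (e.g., reduced or increased". Table 11 itself contains only hold, restart and discontinue rules.

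Section 6 and Section 11.6.2 give one explicit route to a lower dose. A subject who had a DLT is normally discontinued, but if she shows significant response, "they may be eligible to receive ADXS11-001 at a lower dose level for subsequent doses and cycles", by agreement between investigator and sponsor. Separately, the Synopsis and both Section 6 paragraphs mention dose reduction when they list the side effects that end treatment.

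**The concern.** In a 3+3 escalation, a level can be rejected while some subjects on it have had no DLT. Once the RP2D is set one level down, those subjects are on a dose above it. If such a subject is benefiting and starts cycle 2, the Synopsis and the first Section 6 statement give her the RP2D at most. The second Section 6 statement gives her the dose she was on. The section it points to for modification has no step-down for her, and the lower-dose exception does not cover her because she had no DLT.

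At stake is repeated dosing with a live bacterial product at a level the trial has just judged too toxic, in a multi-center study where different sites may rely on different paragraphs.

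**Working it through.** The plan states no figure on this point, so there is none to reproduce. The check compares the rules and then sizes the case.

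**1. Rules side by side.** Suppose 1 x 10^10 CFU is rejected at 2 of 6 DLTs, so the RP2D is 5 x 10^9 CFU and 6 − 2 = 4 subjects are DLT-free. For one of them who responds or has stable disease, cycle 2 is:

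| Source | Dose in cycle 2 |
|---|---|
| Synopsis; Section 6, DLT paragraph | at most 5 x 10^9 CFU |
| Section 6, paragraph on treatment after the initial cycle | 1 x 10^10 CFU |
| Section 11.6.1, read literally | no reduction |
| Section 11.6.2 exception | not applicable (no DLT) |

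If her dose is at or below the RP2D, continuing at the same dose meets both rules. The conflict is confined to a rejected level.

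**2. Dose ratios (Table 4).** Level 2 against Level 1: 1 x 10^10 / 5 x 10^9 = 2. Level 1 against Level -1: 5 x 10^9 / 1 x 10^9 = 5. The second ratio applies only if a Level -1 cohort is enrolled, which Section 6 leaves optional, and becomes the RP2D.

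**3. Subjects per rejected cohort.** The standard rule rejects at 2 or 3 DLTs in 3 subjects, or at 1 in the first 3 followed by 1 to 3 in the next 3.

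- Cohort of 3: 3 − 2 = 1 or 3 − 3 = 0 DLT-free.
- Cohort of 6: 2 to 4 DLTs in all, so 6 − 4 = 2 to 6 − 2 = 4 DLT-free.

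**4. How often it can arise.** The documents give no DLT rate, so p is an assumption. For a level once reached,

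P(rejected with at least 1 DLT-free) = P(2 of 3) + P(1 of 3) × P(at least 1 of the next 3).

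At p = 0.20: 3(0.2²)(0.8) = 0.096; 3(0.2)(0.8²) = 0.384; 1 − 0.8³ = 0.488; total 0.096 + 0.384 × 0.488 = 0.283.

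For the subject also to be eligible to continue, she must respond or have stable disease. With assumed probability r, independent of DLT, each term with k DLT-free subjects is multiplied by 1 − (1 − r)^k.

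| Assumed p | Rejected, at least 1 DLT-free | Mean DLT-free, given rejection | At least 1 eligible to continue, r = 0.25 to 0.75 |
|---|---|---|---|
| 0.05 | 0.026 | 3.14 | 0.015 to 0.025 |
| 0.10 | 0.093 | 3.02 | 0.051 to 0.086 |
| 0.20 | 0.283 | 2.75 | 0.148 to 0.258 |
| 0.33 | 0.530 | 2.36 | 0.253 to 0.472 |
| 0.50 | 0.703 | 1.75 | 0.292 to 0.604 |

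Given rejection, the mean number eligible to continue runs from 1.75 × 0.25 = 0.44 to 3.14 × 0.75 = 2.35.

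**5. Timing.** The DLT window is 28 days, and cycle 2 starts on Day 85 (12 × 7 + 1). A first-three subject may reach cycle 2 before the level has been decided and the RP2D declared. A cap therefore needs wording for that interval too.

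**The case against.** The strongest reply is that the rules can be read together. The Synopsis and the first Section 6 statement set a ceiling for every subject. The second Section 6 statement is a permission, and its own sentence contemplates dose reduction. A careful reader would honor the ceiling, and a site that simply stops the subject breaches nothing. This softens the conflict without removing it. The dose-reduction clause concerns side effects, and a subject tolerating treatment has no textual route from the same dose to a lower one.

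Section 11.6.1 is weaker support than it looks. A reader might infer a flat ban on any reduction. The next sentence there and the title of Table 11 concern drug-related toxicity, and Section 11.6.2 immediately allows a lower dose in one case. It is mainly a toxicity rule with unqualified wording. The Synopsis and Section 6 still disagree without it.

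Controls also exist. Under Section 6 the sponsor makes dose-level decisions in consultation with investigators. Subjects who "experience events described as a DLT in any subsequent treatment cycle will be discontinued from study treatment", and Table 11 holds or stops treatment for toxicity. These limit harm, although the dose-level text addresses cohorts and the starting dose, not a subject already on a rejected level.

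Three further inferences are tempting but unsupported.

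- **Larger numbers from expanded cohorts**, such as 8 DLT-free of 12 or 10 of 15. Escalation is planned for 6 to 12 subjects in total, and DLTs are evaluated only there (Section 6.1). Level 2 can hold at most 12 − 3 = 9 within that plan, and only if the sponsor uses its right to expand; 3 DLTs in 9 would leave 6. Twelve at Level 1 would use the whole escalation, and the roughly 15 at the RP2D come after it is identified.
- **A 5-fold excess in every Level 1 rejection.** If no Level -1 cohort is enrolled or cleared, there is no RP2D against which to state an excess.
- **A contradiction over the remaining cycle 1 infusions** (Weeks 7 and 10, and Week 4 if both DLTs come early). The RP2D ceiling is written for repeated cycles, so nothing in the plan conflicts there.

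Finally, Figure 1 and the text of Section 11.3 are not visible in the copy reviewed. Neither seems likely to settle the point, but the absence of a precedence rule is judged from the visible text.

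**Conclusion.** The inconsistency is real and narrow. For repeat cycles, a DLT-free subject who is benefiting on a level later rejected is capped at the RP2D by two statements and continued at her existing dose by a third, and no visible text says which prevails. Following the third would exceed the RP2D by the ratios in step 2 of the working, under the conditions given there.

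The number affected is small, at most 4 in a rejected cohort of standard size. How often it happens depends on DLT and response rates the documents do not give. The tabled range is too wide to support a claim about likelihood, and shows only that a level can be rejected with such subjects on it. A reader might infer that the escalation result is compromised. It is not: DLTs are counted in the first 28 days of cycle 1, so repeat-cycle dosing changes neither the counts nor the RP2D. The issue is subject safety and consistent dosing across sites, and it should be corrected.

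**What to change.** **Section 6, treatment after the initial cycle.** State that further treatment is given *at the same dose, not exceeding the RP2D (or, before it is declared, the highest dose level not rejected), and on the same schedule*.

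**Section 11.6.1.** State that the no-modification rule does not bar step-down to the RP2D or the Section 11.6.2 exception. Align it with the mentions of dose reduction in the Synopsis and Section 6: either say which reductions for side effects are permitted or remove those mentions.

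**Cost.** Wording only, with no added visits or samples. The clinical downside is that a subject tolerating and benefiting from the higher dose steps down, which the Synopsis and the first Section 6 statement already require for repeat cycles.

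**Optional.** The sponsor may choose to apply the same cap to cycle 1 infusions still due when a level is rejected. That would be a new design rule and is not needed to resolve the inconsistency.
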